6.3.5 Nausea and/or Vomiting

Prophylactic antiemetics before the first dose of the study drug is not recommended. Antiemetics may be used prophylactically as clinically indicated following the occurrence of a first event of TAK-659/Ixazomib drug-related or possibly related nausea and/or vomiting.

6.3.6 Diarrhea

Prophylactic antidiarrheals is not recommended before the first dose of study drugs. However, diarrhea should be managed according to clinical practice, including the administration of antidiarrheals once infectious causes are excluded. Fluid intake should be maintained to avoid dehydration. Fluid deficit should be corrected before initiation of treatment and during treatment.

6.3.7 Edema (Including Periorbital)

Peripheral and periorbital oedema have been observed in patients treated with TAK-659. Management of the event should follow the standard local practice and dose modification as required.

6.3.8 Rash With or Without Pruritus

Prophylactic measures should also be considered if a patient develops a rash (eg, using a thick, alcohol-free emollient cream on dry areas of the body). In the case of rash, the use of a topical or oral steroid (eg, prednisone \leq 10 mg per day or equivalent) is permitted.

In line with clinical practice, dermatology consult and biopsy of Grade 3 or higher rash or any SAE involving rash is recommended. Prophylactic measures should also be considered if a patient has previously developed a rash (eg, using a thick, alcohol-free emollient cream on dry areas of the body or oral or topical antihistamines). A rare risk is Stevens-Johnson Syndrome, a severe and potentially life-threatening rash with skin peeling and mouth sores, which should be managed symptomatically according to standard medical practice. Punch biopsies for histopathological analysis are encouraged at the discretion of the investigator.

6.3.9 Thrombocytopenia

Blood counts should be monitored regularly. Platelet transfusion is allowed to manage severe thrombocytopenia to prevent and minimize bleeding according to ASH/ASCO guidelines and should be proactive to consider functional defects within platelets as a result of Syk/Tec inhibition. Every attempt should be made to adjust the platelet count threshold to a higher level (beginning at 10k without

demonstrated bleeding) at any signs of bleeding, such as oral purpura. Each transfusion episode, including the type of transfusion (platelets), should be recorded.

Ixazomib administration should be modified as noted as per dose modification recommendations in the protocol when thrombocytopenia occurs, after remission has been established by bone marrow testing. In that context, continuation therapy can be reinitiated at a reduced level upon recovery of platelet counts. However, prior to attainment of remission or in the period prior to completion of cycle 2, Ixazomib administration should not be altered due to thrombocytopenia alone, if it can be ameliorated by transfusion to attain minimum platelet count 10,000/uL.

A rare risk is thrombotic thrombocytopenic purpura (TTP), a rare blood disorder where blood clots form in small blood vessels throughout the body characterized by thrombocytopenia and hemolysis, petechiae, fever, or possibly more serious signs and symptoms. TTP should be managed symptomatically according to standard medical practice.

6.3.10 Neutropenia

Blood counts should be monitored regularly. Myeloid growth factors (eg, G-CSF, GM-CSF) may be used to treat severe and/or febrile neutropenia according to ASCO guidelines. However, it should be noted that growth factors are not used routinely in AML patients undergoing chemotherapy and prophylactic use of myeloid growth factors should be avoided during the first cycle of dose escalation.

6.3.11 Anemia

Hemoglobin should be monitored regularly. Packed RBC transfusion is permitted, as necessary, per local institutional practice. In general, RBC transfusion is recommended for all symptomatic patients with anemia or any asymptomatic patients with a hemoglobin \leq 7 to 8 g/dL with the purpose of maintaining the hemoglobin between 8 and 10 g/dL depending on patients' age, symptoms, and comorbid conditions. Each transfusion episode, including the type of transfusion (RBC), should be recorded. Erythropoietic agent use at the investigator's discretion is also allowed and should be administered according to institutional practice.

6.3.12 Hypophosphatemia

Hypophosphatemia has been observed in patients treated with TAK-659. Consider prophylaxis; otherwise refer to dose modification guideline.

6.3.13 Enzyme Elevations (Transaminase, Amylase and Lipase, CPK and LDH Elevations)

Elevations of the enzymes above have been observed. Events are generally asymptomatic and reversible with dose interruption.

LDH elevations have been observed in the majority of patients exposed to TAK-659. These elevations have been asymptomatic and the clinical significance is unknown. No doses have been interrupted due to increased LDH; however, LDH elevations have been observed to be reversible in patients who had TAK-659 interrupted due to other reasons.

6.3.14 Fluid Deficit

Fluid deficit should be corrected before initiation of study drug and during treatment.

6.3.15 Hypotension

Symptomatic hypotension and orthostatic hypotension with or without syncope have been reported with ixazomib. Blood pressure should be closely monitored while the patient is on study treatment and fluid deficit should be corrected as needed, especially in the setting of concomitant symptoms such as nausea, vomiting, diarrhea, or anorexia. Patients taking medications and/or diuretics to manage their blood pressure (for either hypo- or hypertension) should be managed according to standard clinical practice, including considerations for dose adjustments of their concomitant medications during the course of the trial. Fluid deficit should be corrected before initiation of study drug and as needed during treatment to avoid dehydration.

6.3.16 Posterior Reversible Encephalopathy Syndrome

One case of posterior reversible encephalopathy syndrome, which ultimately resolved, has been reported with ixazomib. This condition is characterized by headache, seizures and visual loss, as well as abrupt increase in blood pressure. Diagnosis may be confirmed by magnetic resonance imaging (MRI). If the syndrome is diagnosed or suspected, symptom-directed treatment should be maintained until the condition is reversed by control of hypertension or other instigating factors.

6.3.17 Transverse Myelitis

Transverse myelitis has also been reported with ixazomib. It is not known if ixazomib causes transverse myelitis; however, because it happened to a patient receiving ixazomib, the possibility that ixazomib may have contributed to transverse myelitis cannot be excluded.

6.4 Protocol Therapy Discontinuation

Patients will be informed that they have the right to withdraw from the study at any time for any reason, without prejudice to their medical care. In addition to discontinuation from therapy related to toxicities as outlined in section 6.1, a subject will also be discontinued from protocol therapy and followed up per protocol under the circumstances outlined below. The reason for discontinuation of protocol therapy will be documented on the electronic case report form (eCRF).

- Documented disease progression
- The treating physician determines a change of therapy would be in the best interest of the subject
- The subject requests to discontinue protocol therapy, whether due to unacceptable toxicity or for other reasons
 - If a subject decides to prematurely discontinue protocol therapy (“refuses treatment”), the subject should be asked if he or she may still be contacted for further scheduled study assessments. The outcome of that discussion should be documented in both the medical records and in the eCRF.
- A female subject becomes pregnant
- If protocol therapy is interrupted for ≥ 21 days.
- Protocol violation or non-compliance of the patient
- Study terminated
- If the responsible physician thinks a change of therapy would be best for the patient
- Noncompliance of the patient
- Pregnancy
- Death

6.5 Completion of Study

Patients will be considered to have completed the study if:

- They are followed until death before the end of the survival follow-up window (up to 12 months after discontinuation of study drug for any reason)
- They remain on study treatment free of disease progression at the close of the study, at least 1 year after their first dose of study treatment.
- They continue on to the follow-up for survival after discontinuation of the study drug and reach the end of the 12-month OS follow-up window.
- They discontinue study treatment while in CR and continue on to the follow-up for progression and either experience disease progression before the end of the 12-month follow-up period or reach the end of the follow-up period
- The sponsor investigator or funder (Millennium Takeda) terminates the study

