5.1 Number of Patients

For the phase I portion, up to 18 patients will be enrolled in this study from approximately 2 to 4 study centers in the US. For the phase II portion, 36 patients will be enrolled from these centers.

Patients who are withdrawn from treatment during Cycle 1 for reasons other than toxicity during the phase I portion of the study will be replaced. Patients in the phase II portion of the study, beyond the Simon's two-stage threshold, who are not evaluable for response will be replaced; however, patients who receive at least 1 dose of study drugs, and have measurable disease on bone marrow exam or by biopsy-documented extramedullary tumor at baseline, will be used for futility analyses, including the Simon's two-stage response evaluation.

Duration of Study

Patients, including those who achieve a CR, may receive the combination until they experience disease progression. Patients will discontinue treatment if they have an unacceptable drug-related toxicity. The maximum duration of treatment, however, will be 12 months from Cycle 1 Day 1 (C1D1) unless it is determined that a patient would derive benefit from continued therapy beyond 12 months.

Patients will be followed for 30 days after the last dose of the combination, or to the start of subsequent anticancer therapy, whichever occurs first, to permit the detection of any delayed treatment-related AEs. All patients, including those patients no longer on treatment, will be assessed for survival. Patients who discontinue the study, regardless of reasons for discontinuation, will be followed for up to 12 months after discontinuation of the study drug for survival (every month until death), loss to follow-up, or withdrawal of consent for further follow-up. In addition, information on any subsequent anticancer therapies will be collected during the survival follow-up period. For patients who achieve CR but discontinue study treatment while still in remission, disease progression based upon available local data will also be collected during the survival follow-up period.

The final analyses for the clinical study report may be conducted after all patients enrolled in the study have had the opportunity to complete 3-4 cycles of combination therapy (while still not progressing).

It is anticipated that this study will last for approximately 24-32 months, including 9 to 12 months in the phase I portion, and 15 to 20 months in the phase II portion.

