8.7 Long Term Follow-up Evaluations

All patients, including those patients no longer on treatment, will be assessed for survival. Patients who discontinue the study, regardless of reasons for discontinuation, will be followed for survival every month for up to 12 months after discontinuation of the study drug or until death, loss to follow-up, or withdrawal of consent for further follow-up, whichever comes first. In addition, information on any subsequent anticancer therapies will be collected during the survival follow-period. For patients who achieve CR but discontinue study treatment while still in remission, disease progression data will also be collected during the survival follow-up period.

Follow up may be accomplished via clinic visit, phone call, or other avenues as appropriate.

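### Section 6.5 lets a patient who stopped in CR complete the study at progression, in conflict with the 12-month survival follow-up elsewhere; a site acting on it would censor OS at relapse

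*Combined protocol and SAP*

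**What the plan says.** Section 6.5 lists the conditions under which a patient is regarded as having completed the study. Three of them matter here.

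- **Bullet 1:** death before the end of the survival window.
- **Bullet 3:** "They continue on to the follow-up for survival after discontinuation of the study drug and reach the end of the 12-month OS follow-up window".
- **Bullet 4:** for a patient who stopped drug in CR and is then tracked for relapse, completion comes when they "either experience disease progression before the end of the 12-month follow-up period or reach the end of the follow-up period".

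The follow-up rules elsewhere read differently.

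- **Section 5.1** (under Duration of Study): patients who discontinue, "regardless of reasons for discontinuation, will be followed for up to 12 months after discontinuation of the study drug for survival (every month until death", with loss to follow-up and withdrawal of consent as the other end points. For patients who stop in remission, "disease progression based upon available local data will also be collected during the survival follow-up period".
- **Section 8.7:** "All patients, including those patients no longer on treatment, will be assessed for survival". Monthly contact runs for up to 12 months after stopping drug "or until death, loss to follow-up, or withdrawal of consent for further follow-up, whichever comes first".
- **Footnote 3 of the Phase I and Phase II calendars** repeats the rule for all patients.

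OS runs from study entry to death (Sections 2.2.2 and 13.7.2) and is analysed by Kaplan-Meier. Neither section states a censoring rule.

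**The concern.** A definition of study completion is what a site would naturally use to decide when a patient's record can be closed. Read that way, bullet 4 closes a patient who stopped in CR on the day of relapse, while a patient who stopped for any other reason stays under survival follow-up until death or month 12.

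Censoring OS at relapse is informative, because the risk of death can be expected to rise at relapse. Deaths after relapse drop out of the estimate, and Kaplan-Meier treats the censored patients as if they carried the same risk as those still followed.

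Stopping in CR is also an intended route through the trial. Section 5.3.1 asks for every effort to move responders to transplant after two cycles, and bridging to transplant is part of a secondary objective. OS and mortality at 3 and 6 months are secondary endpoints reported by FLT3 cohort. Section 13.2 says mortality will be weighed in the decision to expand the study.

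**Working it through.** **1. Do the passages conflict?** The bullets in 6.5 must be alternatives, since dying inside the window and reaching its end cannot both happen. Bullet 4 is therefore sufficient on its own.

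| Place | What ends follow-up for a patient who stopped in CR | Role of progression |
|---|---|---|
| 6.5, bullet 4 | Progression, or end of the period | Completes the study |
| 6.5, bullets 1 and 3 | Death, or end of the 12-month OS window | None |
| 5.1 and calendar footnote 3 | Death, loss to follow-up, withdrawal of consent, or 12 months | Collected in addition |
| 8.7 | The same four | Collected in addition |

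Bullet 4 is the only place where progression is terminal.

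**2. Which results are exposed?** Only results that need survival after relapse: OS and later mortality. DOR and TTP end at progression. ORR and the two-stage rules use response. The bullet names CR only, not CRi, CRp or PR.

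**3. How large could it be?** The plan states no OS figure to reproduce, so this step is illustrative. None of these inputs comes from the documents:

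- a share p of patients stops in CR, at month 2;
- median time from stopping to relapse is 3 or 6 months (rate λ1 = ln 2 / median);
- median survival after relapse is 2 or 4 months (rate λ2);
- all other patients have exponential OS with median 5 months (rate λ0 = ln 2 / 5);
- every patient who stops in CR is closed at relapse.

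With u = max(t − 2, 0), OS under full follow-up is

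S(t) = p · [λ2·exp(−λ1·u) − λ1·exp(−λ2·u)] / (λ2 − λ1) + (1 − p)·exp(−λ0·t).

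With censoring at relapse, the only deaths seen are in the other patients, and Kaplan-Meier converges to

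S*(t) = exp{ −∫ λ0·(1 − p)·exp(−λ0·s) / [(1 − p)·exp(−λ0·s) + p·exp(−λ1·u(s))] ds }, integrated from 0 to t.

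Worked case at 6 months, with p = 0.30 and medians of 3 and 2 months: λ1 = 0.2310, λ2 = 0.3466, u = 4. Survival in the CR group is (0.3466 × 0.3969 − 0.2310 × 0.25) / 0.1155 = 0.69. Then S(6) = 0.30 × 0.69 + 0.70 × 0.435 = 51.2%. Numerical integration gives S*(6) = 57.0%, an inflation of 5.8 points.

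Inflation in percentage points, as the range over the four combinations of medians:

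| Share stopping in CR | 3 months | 6 months | 12 months |
|---|---|---|---|
| 4% | under 0.1 | 0.1 to 0.6 | 0.25 to 1.0 |
| 10% | 0.02 to 0.2 | 0.3 to 1.6 | 0.8 to 2.7 |
| 20% | 0.1 to 0.4 | 0.8 to 3.6 | 2.3 to 5.8 |
| 30% | 0.1 to 0.7 | 1.5 to 5.8 | 4.5 to 9.7 |

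A simulation of 400,000 patients per scenario for shares of 10% to 30% agrees: 0.3 to 5.7 points at 6 months, 0.9 to 9.7 at 12 months, and 0.04 to 1.1 months on median OS. In it, 75% to 94% of patients who stopped in CR relapsed inside the window and 50% to 84% had an observed death under full follow-up. Under closure at relapse none of those deaths is seen, because in this model every such death follows a relapse.

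The 4% row reflects the only TAK-659 response data in AML in the protocol (Section 1.4.5, single agent): 1 CR among 26 evaluable patients, 1/26 = 4%. Adding the two CRs with incomplete recovery gives 3/26 = 12%.

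**The case against.** The strongest reply is that the harmful step is not in the text. Section 6.5 says when a patient counts as having completed the study. It does not say that survival contacts stop, and no analysis rule censors OS at completion or at progression. Sections 5.1 and 8.7 and the calendars are the operative instructions, and they are clear. Bullet 4 can be read as a status line for the extra progression data. A relapsed patient who is then followed will in any case meet bullet 1 or bullet 3. All of this stands: bias arises only if a site closes the patient at relapse despite 8.7.

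Two further points also stand. The named mortality landmarks are 3 and 6 months, so the larger 12-month figures should not lead. And the cohorts are small: near 55% survival the standard error is √(0.55 × 0.45 / 20) = 11 points for 20 patients and √(0.55 × 0.45 / 16) = 12 points for 16, larger than any inflation in the table.

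The reply does not remove the conflict. Bullet 4 makes progression sufficient for completion and every other follow-up passage does not. The plan has no stated OS censoring rule to catch the error later, and small cohorts do not turn a one-directional bias into noise.

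**Conclusion.** The point holds as an internal inconsistency that puts secondary OS and later mortality at risk. It is confined to patients who stop drug in CR.

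A reader might infer more. One inference is that the plan instructs sites to stop contacting these patients at relapse. It does not. Another is that OS will be overstated by some definite number of points. The documents do not support that either: the share stopping in CR, the relapse and death rates and the behaviour of sites are all assumed. With 10% to 30% stopping in CR and universal closure at relapse, the inflation is roughly 0.3 to 6 points at 6 months and 1 to 10 at 12 months. If strict CR is as rare as in the single-agent data it is at most about 0.6 points at 6 months, and if sites follow 8.7 it is zero. A third inference is a distorted FLT3-mutant versus wild-type contrast. Unequal CR rates could bias the two OS curves unequally, but Section 13.7.1 says the phase II part is not meant to show differences between disease groups, so this touches description only.

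The correction is worth making because it is trivial, and survival after relapse that was never collected may be hard to recover.

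**What to change.** 1. **Section 6.5, bullet 4:** reword it so that progression ends only the progression follow-up. A patient who stopped in CR then completes the study at death or at the end of the 12-month survival window, as in bullets 1 and 3, with loss to follow-up and withdrawal of consent handled as in Section 8.7.
2. **Section 13.7.2:** add that OS for patients not known to have died is censored at the date last known alive, not at progression or at study completion.

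The cost is two sentences. The monthly survival contacts are already required by Sections 5.1 and 8.7 and the calendars, so no visit or procedure is added. Sample size and decision rules do not change.

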6.6 Protocol Discontinuation

If a subject decides to withdraw from the study (and not just from protocol therapy) all efforts should be made to complete the final study assessments. The site study team should contact the subject by telephone or through a clinic visit to determine the reason for the study withdrawal. If the reason for withdrawal is an adverse event, it will be recorded on the eCRF.

7. STUDY CALENDAR: DOSE ESCALATION COHORTS (PHASE 1)

	Screen	Cycle 1				Cycles 2-4			Cycles 5+			Safety follow up	Long-term follow up	
		-28 days ¹	D 1	D 4	D 8	D 15	D 1	D 8	D 15	D 1	D 8	D 15		
Cycle = 21 days														
REQUIRED ASSESSMENTS														
Informed consent ⁴ , Eligibility criteria	X													
Medical history, Disease characteristics	X	X												
Physical exam ⁵	X	X ⁵		Sx	Sx	X		Sx	X				X	
Ophthalmic Exam ⁶	X					C2				C7D1; q6			X	
Height (screen only); Weight	X	X				X				X			X	
Vital signs (BP, pulse, temperature)	X	X		X	X	X		X	X				X	
ECOG Performance status	X	X				X				X			X	
12-lead ECG ⁷	X	×2			×2				X	X			X	
AEs & concomitant medications ⁸		X		X	X	X		X	X				X	
Drug Diary Review		X		X	X	X				X			X	
LABORATORY ASSESSMENTS⁹														
CBC with diff, platelets, ANC. Chemistry ¹⁰	X	X ¹⁰	X	X ¹⁰	X	X	C2	X	X				X	
Uric acid, Mag, Amylase, Lipase, GGT ¹⁰	X	X ¹⁰	X	X ¹⁰	X	X		X	X				X	
Urinalysis	X				X	X		X	X				X	
Pregnancy test for WOCBP ¹¹	X	X				X				X				
DISEASE ASSESSMENT														
NGS results or submit for NGS testing	X													
Bone marrow biopsy and aspirate ¹²	X				X			C2,4	as indicated					
TREATMENT EXPOSURE														
TAK-659 (Daily ×15 days)			D1-15				D1-15			D1-15				
Ixazomib (Days 1, 8, 15)	X		X	X		X	X	X	X	X	X			
CORRELATIVE STUDIES (SPECIMEN COLLECTION)														
Buccal swab for germline DNA analysis		X												
Bone marrow aspirate for biomarker analyses and PD	X			X ¹³	X			C2,4						
Serum for proteomic analysis		X	X											
Plasma for PK ¹⁴		×2			×2			×2						
BANKING SAMPLES (SPECIMEN COLLECTION)														
Whole Blood ¹⁵		X												
Serum and Plasma ¹⁵		X										X		
FOLLOW-UP														
Survival status, subsequent therapy													X	

Phase I calendar footnotes:

Evaluations/laboratory assessments performed on visit days will occur before dosing unless otherwise indicated. On these days, patients will be instructed to hold dosing until relevant assessments have been completed.

1. Screening assessments performed within 3 days before Cycle 1 Day 1 do not need to be repeated, unless otherwise specified.
2. Safety follow up visit will occur 30 days (+10 days) after the last dose of study drug or before the start of subsequent anticancer therapy (other than hydroxyurea) whichever occurs first.
3. All patients, including those no longer on treatment, will be followed for survival. Patients who discontinue the study will be followed for survival every month for up to 12 months after discontinuation of the study drug until death, loss to follow-up, or withdrawal of consent. Information on subsequent anticancer therapies will also be collected. For patients who achieve CR but discontinue study treatment while still in remission, disease progression based upon available local data will also be collected.
4. Informed consent may be obtained before the Screening period (28 days before Cycle 1 Day 1 dosing).
5. Complete physical examination (PE) will be done at screening, including a neurological exam. Complete PEs will also be done on Day 1 of each cycle and at the 30-day Safety follow up visit. Symptom- or finding-directed PEs will be done on C1D8 and 15 and C2-4 D15.
6. An ophthalmic exam will be done at screening, C2D1, C7D1, q 6 cycles thereafter (± 2 wks), and at 30-day Safety follow up visit. See Section 8.1.
7. Single 12-lead ECGs will be performed within 1 hour predose and 3 hours postdose (± 15 min) on C1D1 and C1D15. All other ECGs will be done only at predose. When the timing of a blood sample coincides with the timing of an ECG, the ECG will be completed first.
8. AEs & con meds will be recorded from first dose of study drugs through 30 days after the last dose of study drugs or the start of subsequent anticancer therapy, whichever occurs first. SAEs will be reported from signing of informed consent through 30 days after the last dose of study drug, even if the patient starts nonprotocol therapy.
9. Laboratory assessments may be conducted within -3 days of the scheduled visit, except PK/PD assessments, or unless otherwise noted. Day 1 visits of Cycle 2 and beyond may be modified by up to 3 days due to inclement weather, holidays, vacations, etc.
10. The hematology and chemistry blood samples for C1D1 may be collected within 3 days before dosing to ensure patient eligibility on Day 1. The percentage of leukemic blast cells should be noted in the hematology panel. Monitor CBCs and CMPs at least twice weekly for the first 2 weeks (including tumor lysis labs) and then check CBCs and CMPs at least weekly to complete the first 2 cycles.
11. Women of childbearing potential: A serum pregnancy test will be done at screening. A urine pregnancy test will be done predose D1 of all cycles, with negative results available prior to dosing. If a negative serum test is done within 3 days of C1D1, the C1D1 urine test will be waived.
12. Bone marrow biopsy and aspirate for disease burden (blast counts), cytogenetics, and cellular composition by flow cytometry will be done at screening. In addition, BM biopsies and/or aspirates will be done to assess disease response at Cycles 1, 2, and 4 between Days 15-21, provided the results are available before Day 1 of the next cycle. After Cycle 4, BM biopsy and/or aspirate assessment will be performed as clinically indicated based on changes in peripheral blood counts, or when it is needed to establish either CR or disease progression. NOTE: a BM biopsy is required only at screening. Residual and/or additional bone marrow samples will be requested for biomarker analysis. In cases when insufficient bone marrow aspirate is collected, peripheral blood will be collected and submitted per the instructions in the CLM.
13. Bone marrow will be done at C1D4 for the 1st 5 patients. Thereafter, BM timing (D4 vs 8) will be determined from the results in the first 5 patients.
14. Blood for PK plasma samples will be collected at: C1D1 (pre-dose, 2-4 hr post-dose), C1D15 (pre-dose, 2-4 hr post-dose), Cycle 2, 3, 4 Day 15 (pre-dose, post-dose anytime during clinic visit). Instruct patient to withhold study drug(s) for that day. The timing of the visit should be planned so that the pre-dose PK draw occurs near the same time as the previous day's dosing. When a blood sample coincides with the timing of an ECG, the ECG will be completed first. Refer to the CLM for detailed instructions on collection, processing, storing, and shipping of PK samples.
15. Whole blood for banking is to be collected at pre-dose C1D1. Serum and plasma for banking are to be collected at pre-dose C1D1 and at the 30-Day Safety Follow up visit. See CLM for collection, processing, labeling and shipping instructions.

8. STUDY CALENDAR: PHASE 2

Cycle = 21 days	Screen	Cycle 1				Cycles 2-4			C 3	Cycles 5+			Safety follow up	Long-term follow up
	-28 days ¹	D 1	D 4	D 8	D 15	D 1	D 8	D 15	D 22	D 1	D 8	D 15	30 days post Tx ²	Q month (±14) ³
REQUIRED ASSESSMENTS														
Informed consent ⁴ , Eligibility criteria	X													
Medical history, Disease characteristics	X	X												
Physical exam ⁵	X	X ⁵		Sx	Sx	X		Sx		X				X
Ophthalmic Exam ⁶	X					C2				C7D1; q6				X
Height (screen only); Weight	X	X				X				X				X
Vital signs (BP, pulse, temperature)	X	X		X	X	X		X		X				X
ECOG Performance status	X	X				X				X				X
12-lead ECG ⁷	X	X						X		X				X
AEs & concomitant medications ⁸		X			X	X		X		X				X
Drug Diary Review		X			X	X				X				X
LABORATORY ASSESSMENTS⁹														
CBC with diff, platelets, ANC. Chemistry ¹⁰	X	X ¹⁰	X	X ¹⁰	X	X	C2	X		X				X
Uric acid, Mag, Amylase, Lipase, GGT ¹⁰	X	X ¹⁰	X	X ¹⁰	X	X		X		X				X
Urinalysis	X			X		X		X		X				X
Pregnancy test for WOCBP ¹¹	X	X				X				X				
DISEASE ASSESSMENT														
NGS results or submit for NGS testing	X													
Bone marrow biopsy and aspirate ¹²	X				X				C3D22 ¹²	as indicated				
TREATMENT EXPOSURE														
TAK-659 (Daily ×15 days)			D1-15			D1-15			D1-15					
Ixazomib (Days 1, 8, 15)		X		X	X	X	X	X		X	X	X		
CORRELATIVE STUDIES (SPECIMEN COLLECTION)														
Buccal swab for germline DNA analysis		X												
Bone marrow aspirate for biomarker analyses and PD	X		X ¹³		X				C3D22 ¹²	@ PD ¹³				
Serum for proteomic analysis		X	X											
Plasma for PK ¹⁴		×2			×2			×2						
BANKING SAMPLES (SPECIMEN COLLECTION)														
Whole Blood ¹⁵		X												
Serum and Plasma ¹⁵		X											X	
FOLLOW-UP														
Survival status, subsequent therapy														X

Phase II calendar footnotes: Evaluations/laboratory assessments performed on visit days need to take place before dosing unless otherwise indicated. On these days, patients should be instructed to hold dosing until relevant assessments have been completed.

1. Screening assessments performed within 3 days before Cycle 1 Day 1 do not need to be repeated, unless otherwise specified.
2. Safety follow up visit will occur 30 days (+10 days) after the last dose of study drug or before the start of subsequent anticancer therapy (other than hydroxyurea) whichever occurs first.
3. All patients, including those no longer on treatment, will be followed for survival. Patients who discontinue the study will be followed for survival every month for up to 12 months after discontinuation of the study drug until death, loss to follow-up, or withdrawal of consent. Information on subsequent anticancer therapies will also be collected. For patients who achieve CR but discontinue study treatment while still in remission, disease progression based upon available local data will also be collected.
4. Informed consent may be obtained before the Screening period (28 days before Cycle 1 Day 1 dosing).
5. Complete physical examination (PE) will be done at screening, including a neurological exam. Complete PEs will also be done on Day 1 of each cycle, and at the 30-day Safety follow up visit. Symptom- or finding- directed PEs will be done on C1D8 and 15 and C2-4 D15.
6. An ophthalmic exam will be done at screening, C2D1, C7D1, q 6 cycles thereafter (± 2 wks), and at 30-day Safety follow up visit. See Sect. 8.1.
7. Single 12-lead ECGs will be done at screening, predose during each cycle and at the 30-day Safety follow up visit. When the timing of a blood sample coincides with the timing of an ECG, the ECG will be completed first.
8. AEs & con meds will be recorded from first dose of study drugs through 30 days after the last dose of study drugs or to the start of subsequent anticancer therapy, whichever occurs first. SAEs will be reported from signing of the informed consent form through 30 days after the last dose of study drug even if the patient starts nonprotocol therapy.
9. Laboratory assessments may be conducted within - 3 days of the scheduled visit, except PK/PD assessments, or unless otherwise noted. Day 1 visits of Cycle 2 and beyond may be modified by up to 3 days due to inclement weather, holidays, vacations, etc.
10. The hematology and chemistry blood samples for C1D1 may be collected within 3 days before dosing to ensure patient eligibility on Day 1. The percentage of leukemic blast cells should also be noted in the hematology panel. Monitor CBCs and CMPs at least twice weekly for the first 2 weeks (including tumor lysis labs) and then check CBCs and CMPs at least weekly to complete the first 2 cycles.
11. Women of childbearing potential: A serum pregnancy test will be performed at screening. A urine pregnancy test will be done predose D1 of all cycles, with negative results available prior to dosing. If a negative serum test is done within 3 days of C1D1, the C1D1 urine test is waived.
12. Bone marrow biopsy and aspirate for disease burden (blast counts), cytogenetics, and cellular composition by flow cytometry will be done at screening. In addition, BM aspirates and/or biopsies will be done to assess disease response at Cycle 1 Day 15 and Cycle 3 Day 22, so that the results are available before Day 1 of the next cycle. In the post-Cycle 3 assessment, aspirate and biopsy are suggested on day 22 (or within 3 days prior to C4D1), simultaneous with the plan to continue onto C4 D1, to serve as record establishing the optimal response/composite CR. Such planning should be guided by the trend of blast reduction observed during Cycles 1, 2. After Cycle 3 assessment, BM biopsy and/or aspirate assessment will be performed as clinically indicated based on changes in peripheral blood counts, or when it is needed to establish either CR or disease progression. NOTE: a BM biopsy is required at screening and post-Cycle 3 D22. Residual and/or additional bone marrow samples will be requested for biomarker analysis. In cases when insufficient BM aspirate is collected, peripheral blood will be submitted per the instructions in the CLM.
13. BM timing (D4 vs D8) will be determined from results in the Phase I patients. At the time of relapse (PD) of any patient who had initially responded to TAK-659, bone marrow aspirate and/or biopsy materials will be collected for biomarker study.
14. Blood for PK plasma samples will be collected at : C1D1 (pre-dose, 2-4 hr post-dose), C1D15 (pre-dose, 2-4 hr post-dose), Cycle 2, 3, 4 Day 15 (pre-dose, post-dose anytime during clinic visit). Instruct patient withhold study drug(s) for that day. The timing of the visit should be planned so that the pre-dose PK draw occurs near the same time as the previous day's dosing. When a blood sample coincides with the timing of an ECG,

the ECG will be completed first. Refer to the CLM for detailed instructions on collection, processing, storing, and shipping of PK samples.

15. Whole blood for banking is to be collected at predose C1D1. Serum and plasma for banking are to be collected at pre-dose C1D1 and at the 30-Day Safety Follow up visit. See CLM for collection, processing, labeling and shipping instructions.

